6.2 IMPORTANT PROTOCOL DEVIATIONS

Handling of iPDs in analysis is included in the DV domain specifications and stored within the TMF in EDMS.

6.3 SUBJECT SETS ANALYZED

The following analysis sets are defined for this trial:

- **Screened set (SCS):**
This patient set includes all patients having signed informed consent.
- **Randomised set: (RS)**
This patient set includes all randomised patients, whether treated or not.
- **Treated Set (TS):**
The Treated Set (TS) consists of patients who are randomized to a treatment group and receive at least one dose of study medication.
- **Pharmacokinetic parameter analysis set (PKS):**
This set includes all patients in the treated set (TS) who provide at least one PK endpoint that was not excluded due to a protocol deviation relevant to the evaluation of PK or due to PK non-evaluability (as specified in the CTP Sec. 7.2.1.). Thus, a patient will be included in the PKS, even if he/she contributes only one PK parameter value for one period to the statistical assessment. Descriptive and model based analyses of PK parameters will be based on the PKS.

Analyses for PK endpoints will be based on the PKS. All other analyses will be based on the TS except for disposition.

Table 6.3: 1 Patient sets analyzed

Class of endpoint	Patient set		
	SCS	TS	PKS
Primary endpoint PK			X
Primary endpoint Safety		X	
Secondary endpoints		X	
Further endpoints Efficacy		X	
Further endpoints PK			X
Safety endpoints		X	
Demographic/baseline characteristics		X	
Disposition	X		

Note that the number of patients with available data for an endpoint may differ. For details, see [Section 6.6](#)

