7.2 PLANNED ANALYSES

7.2.1 General considerations

The following analysis sets will be defined for this trial:

- Treated Set (TS):
The Treated Set (TS) consists of patients who are randomised to a treatment group and receive at least one dose of study medication.
- Per Protocol Set (PPS):
The Per Protocol Set (PPS) will consist of patients from TS considering exclusion from the set based on important protocol deviations.
- Pharmacokinetic Parameter Analysis Set (PKS):
The Pharmacokinetic Parameter Analysis Set (PKS) includes all patients in the Treated Set (TS) who provide at least one PK endpoint that was not excluded due to a protocol deviation relevant to the evaluation of PK or due to PK non-evaluability (as specified in the following subsection ‘Pharmacokinetics’). Thus, a patient will be included in the PKS, even if he/she contributes only one PK parameter value for one period to the statistical assessment.

Descriptive and model based analyses of PK parameters will be based on the PKS. All other analyses will be based on the TS.

Pharmacokinetics:

The pharmacokinetic parameters listed in [Section 2.1](#) and [Section 2.2](#) for nintedanib will be calculated using Phoenix WinNonlin™ software (version 6.3 or higher, [REDACTED]) or SAS® Version 9.4 (or later version) by means of noncompartmental analysis and according to the relevant SOP of the sponsor.

Plasma concentration data and parameters of a subject will be included in the PK analyses, if they are not flagged for exclusion due to a protocol deviation relevant to the evaluation of PK (to be decided no later than in the Blinded Report Planning Meeting) or due to PK non-evaluability (as revealed during data analysis, based on the criteria specified below). Exclusion of a subject's data will be documented in the CTR.

Patients who are considered as not evaluable will be listed with their individual plasma concentrations and individual pharmacokinetic parameters. However they will not be included in descriptive statistics for plasma concentrations, pharmacokinetic parameters or other statistical assessment apart from safety evaluation.

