5.1 PRIMARY ENDPOINT(S)

The primary PK endpoint is the $AUC_{\tau,ss}$ based on sampling at steady state (at week 2 and week 26 visit).

For patients receiving nintedanib in Part A, PK profiles on week 2 and week 26 are planned to be collected. For the primary endpoint $AUC_{\tau,ss}$ the $AUC_{\tau,ss}$ at week 2 will be used. If the week 2 value is missing, then it will be replaced by available $AUC_{\tau,ss}$ at week 26 (or later, if PK visit was postponed). For patients receiving placebo in Part A and nintedanib in Part B, $AUC_{\tau,ss}$ evaluated based on

PK profiles at week 26 (or later, if PK visit was postponed) will be used (which corresponds to week 2 on active treatment).

The primary safety endpoint is the N (%) of patients with treatment-emergent adverse events at week 24, i.e., during the planned double-blind period of the trial.

Thus, the number of patients experiencing at least one adverse event during the double-blind period of the trial will be analyzed, see [Section 7.8](#).

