7.4.1 Primary analysis of the primary endpoint(s)

7.4.1.1 PK endpoint

$AUC_{\tau,ss}$ based on sampling at steady state will be calculated as specified in the CTP Sections 7.2.1 and 7.2.2. For patients receiving nintedanib in Part A, PK profiles on week 2 and week 26 are planned to be collected. For the primary endpoint $AUC_{\tau,ss}$ the $AUC_{\tau,ss}$ at week 2 will be used. If the week 2 value is missing, then it will be replaced by available $AUC_{\tau,ss}$ at week 26 (or later, if PK visit was postponed). For patients receiving placebo in Part A and nintedanib in Part B, $AUC_{\tau,ss}$ evaluated based on PK profiles at week 26 (or later, if PK visit was postponed) will be used as primary endpoint (which corresponds to week 2 on active treatment). See also [Section 6.6.1](#).

To account for potential dose reductions, $AUC_{\tau,ss}$ will be dose normalized by the actual dose taken by the patient corresponding to that PK sampling. The dose normalized $AUC_{\tau,ss}$ for nintedanib (AUC_{τ,ss_D}) will be summarised descriptively.

[figure not shown]
$AUC_{\tau,ss}$ will additionally be derived using population PK modelling (for all patients with at least one valid PK sample). Details of the analysis will be reported separately in the popPKPD report, but the main $AUC_{\tau,ss}$ results also will be included in the CTR.

The 95% CI of nintedanib CL/F_{ss} will be calculated according to company standards.

All PK analyses will be based on the pharmacokinetic analysis set (PKS), see [Section 6.3](#).

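### As written, patients entered directly into open-label Part B to complete the primary PK assessment fall outside the Treated Set, the PK set and the primary AUC rule

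*SAP*

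**What the plan says.** **Why direct entrants would exist.** Protocol 3.1 provides for a rare case in which more PK data are needed after DBL 1. It names two sources: patients still in Part A who are moved early to Part B, and newly screened patients who enter Part B without passing through Part A. Protocol 6.1 confirms that the second group starts open-label treatment from Visit 2.

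**Analysis sets.** SAP 6.3: "The Treated Set (TS) consists of patients who are randomized to a treatment group and receive at least one dose of study medication". Protocol 7.2.1 has the same rule: "The Treated Set (TS) consists of patients who are randomised to a treatment group and receive at least one dose of study medication". On the PK set (PKS), SAP 6.3 says: "This set includes all patients in the treated set (TS) who provide at least one PK endpoint". On everything outside PK it says: "All other analyses will be based on the TS except for disposition". SAP 7.4.1.1 adds: "All PK analyses will be based on the pharmacokinetic analysis set (PKS").

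**Primary AUC rule.** Protocol 7.2.2 and SAP 5.1 and 7.4.1.1 give two branches. Patients on nintedanib in Part A contribute week 2, or week 26 if week 2 is missing. For patients on placebo in Part A who then take nintedanib in Part B, SAP 5.1 says: "PK profiles at week 26 (or later, if PK visit was postponed) will be used (which corresponds to week 2 on active treatment"). There is no third branch.

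**Passages that point the other way.** Protocol 3.2 promises that all PK and clinical data available at DBL 1, or at its update, enter the primary analysis. Protocol 7.2.5 puts every treated patient in the safety analysis. SAP 7 makes direct Part B starters a cohort of their own beside the two randomised groups, but names no analysis set for them.

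**The concern.** The direct entrants are recruited for one purpose, to make up a shortfall in the primary PK data, yet the sets and the AUC rule do not admit them. A programmer who follows SAP 6.3 literally would leave them out of the non-compartmental AUC summary, the confidence interval for CL/Fss and every table run on the Treated Set, including adverse events.

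Two things are at stake. First, the protocol's precision criterion (protocol 7.5) could be missed because the patients added to meet it are not counted. Second, children exposed to open-label nintedanib would have safety data with a promised cohort but no set to hold them.

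Timing adds a little. Under protocol 4.1.5.1 the sponsor unblinds at DBL 1, and these patients arrive only after that, so any rewording prompted by their arrival would follow unblinding.

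**Working it through.** **Step 1: trace a direct entrant through the definitions.**

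| Rule | Condition | Direct entrant |
|---|---|---|
| Treated Set (protocol 7.2.1, SAP 6.3) | randomised, and at least one dose | dosed but not randomised: out |
| PKS (SAP 6.3) | in the Treated Set, with a usable PK endpoint | out |
| PK analyses (SAP 7.4.1.1) | PKS | out |
| Safety tables (SAP 6.3, Table 6.3: 1) | Treated Set | out |
| Primary AUC, branch 1 | nintedanib in Part A | no Part A: does not apply |
| Primary AUC, branch 2 | placebo in Part A, then Part B | no Part A: does not apply |
| Separate cohort (SAP 7) | started directly in Part B | in, but no set named |
| Safety (protocol 7.2.5) | all treated patients | in |

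The last two rows conflict with the rows above them.

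**Step 2: check the period definitions.** The nintedanib and open-label periods in SAP 6.1 and the adverse event periods in SAP 7.8.1 run from nintedanib intake or treatment start, so they can date a direct entrant. The exception is the whole-trial treatment period in SAP 6.1, which starts at the first randomised drug intake.

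**Step 3: reproduce the plan's precision figure.** Inputs from protocol 7.5: gCV 70.8%, n = 20, and a 95% CI within 60% to 140% of the geometric mean.

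- Log-scale SD: σ = √ln(1 + 0.708²) = 0.6374.
- The upper limit binds, because ln 1.4 = 0.336 is smaller than −ln 0.6 = 0.511.
- Largest acceptable observed SD: s* = ln 1.4 × √n / t(0.975, n−1). For n = 20 this is 0.3365 × 4.4721 / 2.0930 = 0.7189.
- Probability = Pr[χ²(n−1) ≤ (n−1)(s*/σ)²]. For n = 20 this is Pr[χ²(19) ≤ 24.17] = 81.03%, which is the entry in Table 7.5: 1. The same formula reproduces all 15 entries of that table.

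**Step 4: leave out k direct adolescent entrants.** Suppose k of them are needed to bring the evaluable adolescents to 20. The documents give no expected number, so k = 1 to 4 is an assumption.

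| k left out | n left | gCV 60% | gCV 70.8% | gCV 80% |
|---|---|---|---|---|
| 0 | 20 | 96.82% | 81.03% | 59.64% |
| 1 | 19 | 94.55% | 74.93% | 52.66% |
| 2 | 18 | 91.20% | 68.03% | 45.71% |
| 3 | 17 | 86.58% | 60.56% | 39.02% |
| 4 | 16 | 80.60% | 52.82% | 32.78% |

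At gCV 70.8% the losses are 81.03 − 74.93 = 6.10, 81.03 − 68.03 = 13.00, 81.03 − 60.56 = 20.47 and 81.03 − 52.82 = 28.21 percentage points.

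**The case against.** **Intent is clear, and the process would expose a shortfall.** SAP 7 gives direct entrants a cohort and protocol 7.2.5 includes all treated patients. Protocol 3.1 uses the updated DBL 1 data only once enough patients have sufficient PK data, so the sponsor would have to count the added patients to reach that point. Protocol 4.1.5.1 also lets the trial team learn how many evaluable patients are missing. This stands. It makes an unnoticed loss unlikely and rules out reading the wording as a deliberate exclusion. It does not repair the definitions.

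**Population PK reaches them.** SAP 7.4.1.1 has AUC additionally "derived using population PK modelling (for all patients with at least one valid PK sample"), with the main results in the trial report. That may well include direct entrants. The same section, however, puts all PK analyses on the PKS, and SAP 6.3 does so for model-based analyses of PK parameters. The non-compartmental summary and the CL/Fss interval stay uncovered either way.

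**Parts of the SAP are not shown.** Further handling there cannot be excluded, but the set definitions and the AUC rule are visible in full.

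**A stronger reading: placebo patients moved early to Part B are excluded too.** A reader might infer this because SAP 7.4.1.1 says "PK profiles at week 26 (or later, if PK visit was postponed) will be used as primary endpoint", while an early switch puts Visit 7 before week 26. The documents do not support it. These patients are randomised, so they are in the Treated Set and can be in the PKS. SAP 5.1 ties the endpoint to the week 26 visit, and protocol 3.1 calls their sampling visit Visit 7, which is that visit. The rule's stated rationale, two weeks on active drug, fits them exactly. Protocol 7.5 keeps all PK data where the length of Part A varies, and no windowing table shown in SAP 6.7 applies to PK. A clarifying clause is enough, and the figures above do not count these patients.

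**Conclusion.** The definitions are wrong as written for direct Part B entrants, and the matter is minor. A literal reading removes them from the non-compartmental AUC summary, the CL/Fss interval and the Treated Set safety tables, against protocol 3.1, 3.2 and 7.2.5 and the cohort sentence in SAP 7.

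The size is conditional. It requires that the rare route is used, and that adolescents entered directly are needed to reach 20 evaluable. With 1 to 4 of them (assumed), the precision probability at gCV 70.8% falls from 81.0% to 74.9%, 68.0%, 60.6% or 52.8%. There is no loss against this criterion if 20 evaluable adolescents are otherwise available, or if the added patients are under 12. A reader should not infer that the trial is expected to miss its precision target: the documents give no basis for the number of direct entrants.

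The risk of bias is small, because the PK analysis is descriptive and compares no treatments.

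**What to change.** 1. In SAP 6.3 and protocol 7.2.1, define the Treated Set as all patients with at least one dose, whether randomised or entered directly into Part B, and derive the PKS from it. Keep the Part A comparisons and the MMRM on randomised treated patients.
2. In SAP 5.1, 6.6.1 and 7.4.1.1 and protocol 7.2.2, add to the AUC rule that a patient whose first nintedanib is open-label contributes the Visit 7 profile after two weeks of open-label treatment, or a later one if the visit is postponed. This also settles any doubt about early-switched placebo patients.
3. Show the primary PK summary pooled and by cohort.
4. In SAP 6.1, start the whole-trial treatment period at the first trial drug intake, without requiring that intake to be randomised.

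The cost is wording only, with no extra patients, visits or samples. The downside is one more analysis set to maintain, and a pooled PK summary that mixes direct open-label entrants with randomised patients, which is why the display by cohort is needed.

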6.5 POOLING OF CENTRES

This section is not applicable because centre/country is not included in the statistical model.

6.6 HANDLING OF MISSING DATA AND OUTLIERS

In general, missing data will not be imputed. Exceptions are detailed in the subsequent subsections.

6.6.1 Primary endpoint

Missing data and outliers of PK data are handled according to (7). For patients receiving nintedanib in Part A, PK profiles on week 2 and week 26 are planned to be collected. For the primary endpoint $AUC_{\tau,ss}$ the $AUC_{\tau,ss}$ at week 2 will be used. If the week 2 value is missing, then it will be replaced by available $AUC_{\tau,ss}$ at week 26 (or later, if PK visit was postponed).

Missing or incomplete AE dates will be imputed according to BI standards (see “Handling of missing and incomplete AE dates”) (8).

6.6.2 Secondary and further endpoints

6.6.2.1 Change from baseline endpoints

The statistical Mixed effect Model for Repeated Measures (MMRM) used for the analysis of continuous secondary endpoints allows for missing data, assuming they are missing at random.

Item-level data for the PedsQL™ questionnaires will be handled according to the instructions provided by the instrument developer (see [Appendix Section 9.1](#)).

If no FVC measurement prior to first trial drug intake is available, the baseline FVC value will be imputed with the earliest FVC value obtained after (but on the same day as) the first trial drug intake.

According to (7), other missing biomarker data (NOS - no sample available, NOR - no valid result, NOA - not analysed) will not be imputed.

Data below or above the limit of quantification (BLQ or ALQ) for biomarkers will be handled as follows:

- BLQ data will be replaced by 0.5 LLOQ (lower limit of quantification). Hereby LLOQ will be the maximum used lower reference limit for classification of BLQs. All values lower than LLOQ will be imputed (regardless of whether they are classified as BLQ or not).
- ALQ data will be replaced by ULOQ (upper limit of quantification), if ULOQs are available and are greater than observed study values (i.e. the highest solution will be applied for the measurement). Otherwise, ALQ data will be excluded from the analysis.

6.6.2.2 Time-to-event endpoints

In the analyses of the time-to-event endpoints, missing or incomplete data will be managed by standard survival analysis techniques (i.e. censoring). If a patient has no event then he will be censored as described in [Section 5.2.2](#).

A missing or incomplete date of death will be imputed/completed that the derived date is the earliest possible date which is on or after date of onset of the fatal AE, and on or after treatment start (in case this AE is treatment-emergent), and on or after derived date of last contact.

For the time to first respiratory-related hospitalization, or time to first acute ILD exacerbation, in case of partially missing dates, the following imputation will be done:

- If day is missing, then imputed day will be the 15th of the month
- If day and month are missing, then imputed date will be the 1st of July of the (non-missing) year
- If year is missing, date will not be imputed

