5.2.2.11 Time to first respiratory-related hospitalization over the whole trial

Time to first respiratory-related hospitalization assessment will be based on the date of hospitalization collected on a specific hospitalization eCRF page.

For those patients who experience a respiratory-related hospitalization, time to first respiratory-related hospitalization [days] will be computed as:

- Date of first respiratory-related hospitalization – date of first drug intake + 1

Patients who did not experience any event during their trial participation will be censored according to the mechanism for censoring as described in [Table 5.2.2.11: 1](#).

Table 5.2.2.11: 1 Censoring Rules for Time to first respiratory-related hospitalization over the whole trial

Rule #	Situation	Outcome (event or censored)	Date of event or censoring
1	Patient had a documented respiratory-related hospitalization and the date of the event is known	Event	Date of event
2	Patient had a documented respiratory-related hospitalization and the date of the event is unknown	Event	Imputed date of event (imputation see Section 6.6.2.2)
3	Patient did not have a documented respiratory-related hospitalization (no matter whether the patient is alive or died or patient status is unknown)	Censored	Date of last contact when the patient was known to be alive and event free

5.2.2.12 Time to first acute Interstitial Lung Disease (ILD) exacerbation or death over the whole trial

For those patients who either experience acute ILD exacerbations or who die due to any cause at any point in the study, time to first acute ILD exacerbation or death [days] will be computed as:

- Date of first documented acute ILD exacerbation or death (whichever occurs earlier) – date of first drug intake + 1

Patients who did not experience any event during their trial participation will be censored according to the mechanism for censoring as described in [Table 5.2.2.12: 1](#).

Table 5.2.2.12: 1 Censoring Rules for Time to first acute ILD exacerbation or death over the whole trial

Rule #	Situation	Outcome (event or censored)	Date of event or censoring
1	Patient had a documented acute ILD exacerbation or died and the date of the event is known	Event	Earliest Date of event

Table 5.2.2.12: 1 Censoring Rules for Time to first acute ILD exacerbation or death over the whole trial (continued)

Rule #	Situation	Outcome (event or censored)	Date of event or censoring

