6.6.3.3.2 Treatment interruptions

For the definition of off-treatment periods an incomplete start or end date for a treatment interruption will be imputed the same way as specified for time-to-event analyses in [Section 6.6.2.2](#). For duration of interruption no imputation will be applied, i.e. interruptions with missing or incomplete start or end date will have duration missing. Overall duration of interruptions per patient will be missing in these cases as well.

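### The imputation rule for partial hospitalisation, exacerbation and interruption dates has no bounds and can produce impossible times; a minor but real drafting error

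*SAP*

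**What the plan says.** SAP 6.6.2.2 introduces the rule with "For the time to first respiratory-related hospitalization, or time to first acute ILD exacerbation, in case of partially missing dates". It then gives two steps: "If day is missing, then imputed day will be the 15th of the month", and "If day and month are missing, then imputed date will be the 1st of July of the (non-missing) year". If the year is missing, nothing is imputed. No condition ties the result to first drug intake, last contact or death.

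Rule 2 in each of Tables 5.2.2.11: 1 and 5.2.2.12: 1 sends events with an unknown date to this section. The times are then calculated as "Date of first respiratory-related hospitalization – date of first drug intake + 1" and, for the composite in SAP 5.2.2.12, "Date of first documented acute ILD exacerbation or death (whichever occurs earlier) – date of first drug intake + 1".

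SAP 6.6.3.3.2 extends the rule when off-treatment periods are defined: "an incomplete start or end date for a treatment interruption will be imputed the same way as specified for time-to-event analyses". Table 5.4.3: 1, rule 2, uses the dates from 6.6.3.3 for time to first treatment interruption. Interruption durations are not imputed and are left missing.

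Two neighbouring rules are bounded. An imputed date of death (6.6.2.2) may not precede onset of the fatal AE, last contact or, for a treatment-emergent AE, treatment start. An imputed last drug intake (6.6.3.3.1) may not follow death or last contact.

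**The concern.** Under the SAP's own formula, an event on the day of first intake has time 1, so no event after first intake can have a smaller value. A midpoint rule without bounds can return zero or a negative number, and the SAP does not say whether such a patient is then dropped, counted at time zero or handled in some other way. That choice would fall to the programmer. The same rule can place a hospitalisation after the patient's death, or reverse the start and end of an interruption.

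The bounds on the adjacent rules show that the safeguard was known and that this rule lacks it. With about 20 patients on nintedanib and 10 on placebo, each patient is 5 or 10 percentage points of an arm, so even one mishandled record would be visible in a Kaplan-Meier curve.

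**Working it through.** The documents state no figure on this point, so there is none to reproduce. The check applies the SAP's formula to the dates that the rule produces.

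**Worked examples** (time = event date − first intake + 1)
- Check value: event on the day of first intake gives 0 + 1 = 1.
- First intake 20 March 2021, event March 2021 with day missing: imputed 15 March; −5 + 1 = **−4**. An event after first intake in that month can only be day 1 to 12.
- First intake 1 October 2020, event 2020 with day and month missing: imputed 1 July; −92 + 1 = **−91**. The possible range is day 1 to 92.
- Interruption starting 20 March, ending in March with day missing: the end becomes 15 March, **5 days before the start**. With the start day missing and the end on 10 March, the start falls 5 days after the end.

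**How far out the date can be**, over all 365 days of a non-leap year, when the event shares its month (day missing) or year (day and month missing) with the reference date

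| Partial date | Reference date | Days of the year affected | Worst case |
|---|---|---|---|
| Day missing | First intake on the 16th or later | 185/365 = 50.7% | time −15 |
| Day and month missing | First intake 2 July to 31 December | 183/365 = 50.1% | time −182 |
| Day missing | Death or last contact on the 1st to 14th | 168/365 = 46.0% | 14 days late |
| Day and month missing | Death or last contact before 1 July | 181/365 = 49.6% | 181 days late |

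These shares are conditional on sharing the month or year. They are not expected frequencies in the trial.

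**Share of partial dates falling outside follow-up.** Assume first intake is uniform over the calendar and events are uniform over F days of follow-up. Let P be the length of the unknown unit (365 days if day and month are missing, about 30 if only the day is), with the imputed date at its midpoint.
- Too early: follow-up starts in the second half of a unit (probability 1/2) and the event falls in what is left of that unit (on average P/4 days out of F). This gives 1/2 × (P/4)/F = P/(8F).
- Too late: the same, by symmetry.
- Total: P/(4F), for F of at least about P/2.

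| Follow-up | Day and month missing | Day missing |
|---|---|---|
| 26 weeks (182 days) | 365/728 = 50% | 30/728 = 4.1% |
| 52 weeks (364 days) | 365/1456 = 25% | 30/1456 = 2.1% |
| 76 weeks (532 days) | 365/2128 = 17% | 30/2128 = 1.4% |

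A simulation under the same assumptions gave 25.0% and 2.1% at 52 weeks.

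**After bounding** to the interval from first intake to the earlier of last contact and death, the two event examples move from −4 and −91 to day 1.

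**The case against.** The case on the other side is mainly about how often this can happen and how much it moves.

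- **Partial dates should be rare.** Protocol 8.3.1 makes AE onset dates mandatory in source, the Flow Chart has hospitalisations and exacerbations reviewed at each scheduled clinic visit from Visit 2, and Protocol 5.1.3 provides a dedicated hospitalisation page. A missing month is much less likely than a missing day. This stands, although the onset requirement does not mention interruption dates.
- **Some cases are harmless.** The composite takes the earlier of exacerbation and death, so an exacerbation imputed after a known death changes nothing. SAP Section 5 lets an imputed AE date extend last contact, so an exacerbation can carry last contact with it. Dates before first intake are not rescued by either provision.
- **A bound may exist elsewhere.** SAP 6.6.1 sends incomplete AE dates to a company standard, and SAP 6.1 leaves further details to an ADS plan. Neither is available here, so this cannot be excluded. But 6.6.2.2 defers to neither, and because exacerbations are AEs, two rules may cover one date.
- **The consequence is small.** SAP 7.5.2.2 plans Kaplan-Meier estimates at 24 and 52 weeks with no test. A misdated event is still an event, and the estimate moves materially only if the error crosses one of those times or leaves follow-up. The 5 or 10 points is the weight of one patient, not the effect of the rule.

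Two stronger readings are tempting. A reader might infer that most month-missing dates are impossible, since the same model with only 24 weeks of follow-up gives 1 − 168/365 = 54%. But these endpoints run over the whole trial, and Protocol 3.2 expects at least 26 weeks of treatment and about 12 months of nintedanib exposure on average. A reader might also count interruptions with both days missing in one month, which start and end on the 15th. Those dates are not impossible, and no false zero duration follows because the duration is left missing.

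**Conclusion.** The rule is wrong as written, and the error is minor. Followed literally, it produces times that the SAP's own definition does not allow, and neither document supplies a correction. The affected outputs are the descriptive Kaplan-Meier estimates for respiratory hospitalisation and for exacerbation or death, time to first interruption, and the boundaries of off-treatment periods. Interruption durations are not affected.

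Given a date with day and month missing, about one in four falls outside a 52-week follow-up. With only the day missing, it is about one in fifty. Both figures rest on uniform first-intake and event dates. The number of partial dates is not stated in the documents and is probably small, so the expected effect on the trial's results is very small.

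**What to change.** Add to SAP 6.6.2.2:

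> For events known to have occurred after first drug intake, an imputed date before first drug intake is set to the date of first drug intake. An imputed date after death or after last contact (derived without the imputed date) is set to the earlier of these. The result must stay within the known month or year.

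Last contact has to be derived without the imputed date because SAP Section 5 would otherwise let the imputed date move its own upper bound.

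Add to SAP 6.6.3.3.2:

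> An imputed interruption start may not be before first drug intake or after the interruption end, and an imputed end may not be before the start. An imputed date that breaches one of these limits is set to the known date that it breaches.

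State also that, for the exacerbation endpoint, 6.6.2.2 takes precedence over the company AE-date standard cited in 6.6.1.

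The cost is a few sentences in the SAP and a short change to the date derivation. No new data are needed, and neither the design nor the endpoint definitions change.
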